#### **SPECIFIC AIMS**

Concisely state the objectives of the study and the hypothesis being tested.

The proposed study will examine interpersonal post-prandial responses to specific foods and meals based on personal features and characterize their variability across study groups. We propose to conduct a recall-by-genotype study among individuals with extremes genotypes influencing dietary intake from the Partners Healthcare Biobank to study the glycemic and metabolomic responses to a standardized and an election meal in a full-day clinic visit.

The specific objective of the PREMIER study is to carry out an interventional dietary study to measure the response of blood glucose and other biomarkers to a standardized meal or an election meal of varying nutritional content.

The specific hypothesis of this study is that deep molecular, physiological, and behavioral profiling can identify mechanisms underlying variable responses to specific foods and meals. The study will deliver preliminary data to link underlying genetic influences for food preferences with variable metabolic responses to different types of meals. If successful, it is foreseen that this data could be used to inform personalized dietary interventions focused on optimizing substrate metabolism and body weight.

#### **BACKGROUND AND SIGNIFICANCE**

Provide a brief paragraph summarizing prior experience important for understanding the proposed study and procedures.

Dietary intake is a major driving force behind the escalating obesity and type 2 diabetes (T2D) epidemics and is shaped by the confluence of social and environmental factors acting on a background of inherited biological differences (Atasoy et al., 2012; Rankinen and Bouchard, 2006; Swinburn et al., 2011; van der Klaauw and Farooqi, 2015). To inform more effective obesity and T2D prevention strategies, it is crucial to better understand the biological, environmental, and social factors that influence how people interact and respond to specific foods (Cefalu et al., 2015; Hawkes et al., 2015; Unwin et al., 2010; White, 2016).

In a recent large-scale genome-wide association study, our research team has identified 96 genomic regions associated with overall variation in dietary intake (Merino et al., 2019). These findings provided insight into specific brain regions, cell types, and neural processes regulating food intake and intermediary metabolism. However, the clinical utility of this information remains largely unknown. Two recent advances in the genetics of complex traits could offer translational opportunities. First, the development of modern computational methods to cluster genetic variants based on underlying similarities, and collapsing them into cluster-specific polygenic scores (PSs), represents an efficient approach to capture genetic susceptibility and has the potential to deliver clinical benefit through enhanced capacity to maximize response to tailored behavioral interventions for the prevention and management of obesity and T2D (Udler et al., 2018; Udler et al., 2019). Second, the advent of recall-by-genotype studies, an approach to recall participants from clinical studies based on their specific genotype, can be used to identify people with the desired genotypes for clinical interventions and deep phenotyping (Corbin et al., 2018).

Connecting knowledge about human genetic variants with information from circulating metabolites can be particularly useful in understanding the mechanisms by which some people experience a detrimental response to specific foods. Large clinical trials have shown that close adherence to healthy lifestyle interventions can prevent or delay the progression to T2D by ~50% (Knowler et al., 2002; Pan et al., 1997; Ramachandran et al., 2006; Tuomilehto et al., 2001). However, large variability exists in response to dietary interventions (Korem et al., 2017; PW; Spector; Zeevi et al., 2015). Understanding the links between food intake signaling mechanisms and intermediate metabolism may help optimize the beneficial impact of dietary interventions and strengthen adherence to personalized dietary recommendations.

## **RESEARCH DESIGN AND METHODS**

Briefly describe study design and anticipated enrollment, i.e., number of subjects to be enrolled by researchers study-wide and by Partners researchers. Provide a brief summary of the eligibility criteria (for example, age range, gender, medical condition). Include any local site restrictions, for example, "Enrollment at Partners will be limited to adults although the sponsor's protocol is open to both children and adults."

We will recruit 30 healthy adults, 21-65 years of age for this study. Participants will be recruited from the Partners Healthcare Biobank, an electronic health records biorepository with clinical

and genetic data from  $\sim$ 36,000 individuals, who have consented to re-contact and through Patient Research Invitation (PRI). Participants will be excluded if they:

- Refuse or are unable to give informed consent to participate in the study.
- Have type I or type II diabetes mellitus or are taking medications for type II diabetes mellitus. Those not on medications but having a capillary glucose level of >126 mg/dL based on fingertip glucose measurements will be excluded.
- Are obese (BMI>30.0kg/m^2) or underweight (BMI $\leq 18.5$ kg/m^2).
- Have had a heart attack (myocardial infarction) or stroke in the last 3 years.
- Have had cancer in the last 3 years, excluding skin cancer.
- Have an ongoing inflammatory disease i.e. Rheumatoid arthritis, systemic lupus erythematosus, polymyalgia and other connective tissue diseases.
- History of cirrhosis and/or aspartate aminotransferase (AST) or alanine aminotransferase (ALT) more than 3 times the upper limit of normal (ULN).
- No known sickle cell disease or anemia.
- Are currently suffering from acute clinically diagnosed depression.
- Currently taking or intending to take during the study duration any medication known to affect glycemic parameters, such as glucocorticoids or fluoroquinolones.
- Are unable to fast from 9pm the night before the clinic visit until 9am on the clinic day
- Are pregnant or breastfeeding.
- Are participating in another clinical study.
- Are vegan, suffering from an eating disorder or unwilling to eat foods that are part of the study.

Briefly describe study procedures. Include any local site restrictions, for example, "Subjects enrolled at Partners will not participate in the pharmacokinetic portion of the study." Describe study endpoints.

Eligible participants who have reconsented to contact from the Partners HealthCare Biobank with desired genotypes and through Patient Research Invitation (PRI) will be contacted by study coordinators via our IRB approved contact letter.

Eligible participants will then be invited to attend the Translational and Clinical Research Center at MGH for their visit. Before the visit, participants will be sent pre-visit instructions, questionnaires and consent forms. Informed consent will be taken at the visit. After participants have given informed consent to take part they will have a fasting blood sample taken. In the event that a participant does not provide informed consent, no samples will be collected from the participants. Participants will then undergo a brief medical examination to measure BP, waist circumference, weight and height. During the clinical visit, participants will be cannulated, consume a set breakfast and an election lunch and provide blood samples at 9 time points (at baseline, [Breakfast meal], 30, 60, 120, 180, 240, [Lunch meal], 270, 300, 360 minutes (all minute intervals are relative to their first bite of the breakfast test meal)).

The subjects will also be asked to collect a stool sample the day of the visit or within 48 hours. In the event that a participant cannot produce a stool specimen during the visit, arrangements will be made to have the stool sample returned by mail. The participant will be given a stool collection kit containing illustrated instructions and all materials required to collect the stool specimen. The stool specimens will be collected into preservative-containing specimen tubes

using standard Human Microbiome Project protocols. There are no discernible risks associated with stool collection.

For studies involving treatment or diagnosis, provide information about standard of care at Partners (e.g., BWH, MGH) and indicate how the study procedures differ from standard care. Provide information on available alternative treatments, procedures, or methods of diagnosis.

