If a subject withdraws consent to the use of donated biological samples, any retained samples will be disposed of/destroyed. If these samples have already been used for data analysis (e.g. sequencing or metabolite measurement) it will not be possible to destroy this data and it will remain as a part of the study, but any data that is retained will be anonymized.

The Principal Investigator:

- Will ensure subjects' withdrawal of informed consent is recorded. Will ensure that biological samples from that subject, if stored at the study site, are immediately identified, disposed of/destroyed and the action documented.
- Will ensure that the laboratory(ies) holding the samples is/are informed about the withdrawn consent immediately and that samples are disposed of/destroyed and the action documented.

All participants must consume the baseline breakfast and provide baseline fasting bloods. Failure to meet these two requirements will result in termination of continued study participation as other endpoints will be unevaluable. If any other sample collections, dietary interventions, or blood timepoints are missed or unable to be completed, the subjects may continue with participation and these missing items will be logged by the study staff.

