STATISTICAL ANALYSIS PLAN

Answer all questions accurately and completely in order to provide the PHRC with the relevant information to assess the risk-benefit ratio for the study. Do not leave sections blank.

PRINCIPAL/OVERALL INVESTIGATOR

[name] Research Staff, Diabetes Unit and Center for Genomic Medicine Richard B. Simches Research Center Massachusetts General Hospital (MGH) [name]

PROTOCOL TITLE

PREMIER: PREvention of Metabolic Illness through prEcision nutRition

FUNDING

Pilot and Feasibility Award program from the Nutrition Obesity Research Center at Harvard (NORCH)

VERSION DATE

04/22/2025

NCT ID number:

2019P002638

STATISTICAL ANALYSIS PLAN

Baseline characteristics will be reported as mean and standard deviation for continuous measures and number and percent for categorical variables. Characteristics will be reported stratified by genetic category (meal 1 and meal 2) and by meal selection (meal 2 only).

The primary exposures are genetic category (meal 1 and meal 2) and meal selection (meal 2). The co-primary outcomes are response profiles of insulin and glucose after meal 1 (0-180 minutes) and meal 2 (240-360 minutes). For each outcome, we will analyze the post-prandial response profile using linear mixed effects models adjusting for age, sex, BMI, three genetic principal components, and time, with a random effect for participant and a genetic category-by-time interaction to assess for between-group differences.

Secondary outcomes will include incremental area under the curve of insulin and glucose after each meal, meal selection, and lipid levels at 240 minutes after the first meal.

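### Does the plan need a rule for meal 2 time when lunch does not start exactly 240 minutes after breakfast?

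*Protocol*

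**What the plan says.** The Protocol, under Research Design and Methods, sets out one full-day visit with a set breakfast, a chosen lunch and nine blood draws. After baseline, the order is "Breakfast meal], 30, 60, 120, 180, 240, [Lunch meal], 270, 300, 360 minutes". All of these times share one origin: "all minute intervals are relative to their first bite of the breakfast test meal". Lunch has a place in the sequence but no stated minute or window.

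The SAP names as co-primary the "response profiles of insulin and glucose after meal 1 (0-180 minutes) and meal 2 (240-360 minutes"). The exposures are also tied to meals: "The primary exposures are genetic category (meal 1 and meal 2) and meal selection (meal 2"). The model is a linear mixed model with time as a covariate, "a random effect for participant and a genetic category-by-time interaction to assess for between-group differences". The SAP does not say whether time is scheduled or actual, and gives no separate origin for meal 2. Incremental area under the curve (iAUC) after each meal is secondary.

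On deviations, the Protocol says in the text just before Foreseeable Risks and Discomforts that a participant may continue after a missed or uncompleted item, and that "these missing items will be logged by the study staff". Late items are not mentioned. The planned size is stated as follows: "We will recruit 30 healthy adults, 21-65 years of age for this study".

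**The concern.** Breakfast timing is exact by construction, because its first bite is minute zero. Lunch has no such anchor. If lunch starts d minutes after the 240-minute draw and the later draws stay on the breakfast clock, they fall at 30 − d, 60 − d and 120 − d minutes after lunch. With d = 10 the first post-lunch sample is a 20-minute value labelled as a 30-minute value, on a part of the curve that can be steep.

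Participants choose their lunch, and meal selection is a primary exposure for meal 2. If one meal took longer to serve or start, the later group's curve would move to the right, typically lower at 270 minutes and higher at 360. Some of that shift could be read as a metabolic difference. A co-primary outcome would be affected, the choice between nominal and actual time would be left until after data collection, and an unrecorded start time could not be recovered. Meal 1 is not affected.

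**Working it through.** **What the text implies.** The listed times are baseline, 30, 60, 120, 180, 240, 270, 300 and 360, which gives the stated nine. Lunch comes directly after the 240 draw, and the SAP window for meal 2 opens at 240. Read together, lunch is meant to start at about 240. The 240 sample is then the pre-meal value, and the later draws fall at 270 − 240 = 30, 300 − 240 = 60 and 360 − 240 = 120 minutes after lunch.

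**Assumed inputs.** The documents give no delay, curve or SD, so all of these are assumptions:
- Glucose rise x minutes after lunch: f(x) = 40 (x/p) exp(1 − x/p), which peaks at 40 mg/dL at p = 30, 45 or 60 minutes. The pre-meal value is 0.
- Lags of 0 to 15 minutes. Between-group differences are one 5-minute step: 0 v 5, 5 v 10 or 10 v 15.
- Between-person SD of 15 to 25 mg/dL, residual SD s of 10 to 25, and 15 v 15 of the 30 participants.

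**Random lag, the same in both groups.** By simulation, a lag uniform on 0 to 15 minutes adds an SD at 270 of 2.1, 3.2 or 3.4 mg/dL (p = 30, 45, 60). The worst case is √(15² + 3.4²)/15 − 1 = 2.5%. The smallest, with a lag on 0 to 10 minutes, is about 0.05%.

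**A 5-minute lag difference between groups, nominal time.**

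| | p = 30 | p = 45 | p = 60 |
|---|---|---|---|
| Change at 270 (mg/dL) | −0.62, −2.16, −4.24 | −2.56, −3.67, −5.02 | −3.11, −3.90, −4.80 |
| Change at 360 | 1.05, 1.17, 1.30 | 1.43, 1.49, 1.54 | 1.22, 1.22, 1.20 |
| Mean of four draws | 0.72, 0.34, −0.19 | −0.05, −0.39, −0.81 | −0.51, −0.79, −1.12 |
| Linear slope per 120 min | 1.57, 2.22, 3.04 | 2.45, 2.86, 3.33 | 2.31, 2.53, 2.78 |

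Each cell lists 0 v 5, 5 v 10 and 10 v 15. For example, at p = 45 with 0 v 5, f(25) − f(30) = 34.7 − 37.2, or −2.56 before rounding.

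- Single draw at 270: SE = SD √(2/15), which is 5.5 to 9.1. The shift is 0.62/9.13 = 0.07 to 5.02/5.48 = 0.92 SE.
- Slope: the sum of squares of times 0, 30, 60 and 120 is 7,875. The SE of the slope difference per 120 minutes is 120 s/√7,875 × √(2/15), which is 4.94 at s = 10 and 12.34 at s = 25.
- Carry-over from meal choice to genetic category-by-time, if choice differs by 30 to 50 percentage points between genetic groups: 0.3 × 1.57 = 0.47 to 0.5 × 3.33 = 1.67 mg/dL. That is 0.47/12.34 = 0.04 to 1.67/4.94 = 0.34 SE.
- If the lag itself differed by genetic category: 1.57/12.34 = 0.13 to 3.33/4.94 = 0.67 SE.

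**Would actual time since lunch help?** The same linear slope contrast, with the 240 sample at time 0 and the later draws at their true minutes since lunch:

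| | Nominal | Actual |
|---|---|---|
| p = 30 | 1.57, 2.22, 3.04 | −0.10, 0.57, 1.75 |
| p = 45 | 2.45, 2.86, 3.33 | 1.53, 2.20, 3.17 |
| p = 60 | 2.31, 2.53, 2.78 | 2.04, 2.58, 3.31 |

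If the 240 sample is instead given its true time of −d, all four times move by the same amount and the slope contrast does not change.

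**iAUC, one 5-minute step.** At nominal times it moves by −4.2% to +4.4%. On actual time, cut at a common 105 minutes, it moves by −0.5% to +2.9%. The gain is not uniform: at p = 45 with 0 v 5 it goes from +0.2% to +0.9%. The common cut also drops 15 of the 120 minutes for everyone.

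**The case for a change.** The best case for a rule is that it is cheap and should be fixed before results are seen. It would need a few clock times and one SAP sentence. Neither document has such a rule, and the Protocol's provision for missed items does not cover a late lunch. Meal selection is a primary exposure, so a delay that depended on the chosen meal would be mixed with the effect under study. At a single time point the shift could reach 0.9 SE on the assumed curves.

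The silence in the text is real, and a start time is worth having. The rest weakens on inspection. The 0.9 SE figure is the least favourable corner of the assumptions, for a contrast by meal selection at 270 alone, and the SAP states no meal-selection-by-time term. A meal-selection effect averaged over the four draws moves by 1.1 mg/dL or less. One sentence would not be enough either: with linear time, actual minutes do not reliably remove the shift, and with categorical time they cannot enter without bins or a chosen curve. Timing the draws from lunch would keep a 120-minute window but make time since breakfast vary. The single breakfast clock also fits the secondary lipid outcome at 240 minutes after the first meal.

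**Conclusion.** No change to the plan follows. Followed as written, the schedule gives a pre-meal sample at 240 and draws at about 30, 60 and 120 minutes after lunch. What is missing is operational detail that study staff and analysts can fill sensibly.

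Harm needs two conditions, neither of which the documents suggest: a late lunch, and lateness that differs by chosen meal or genetic category. For lateness by chosen meal to reach the genetic category-by-time test, meal choice must also differ between genetic groups. On the assumed inputs, a random lag costs at most 2.5% in SD, and carry-over from a 5-minute difference between meals is 0.04 to 0.34 SE. A 5-minute difference by genetic category itself would give 0.13 to 0.67 SE, but nothing in the documents suggests one. Actual-time modelling shows no dependable gain for the co-primary analysis, and the iAUC rule is a trade-off in a secondary outcome. For a 30-person pilot meant to give preliminary data, that does not justify an amendment.

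Noting the clock time of the first bite of lunch and of the later draws is ordinary good record-keeping. It may already be on the case report form, which is not among the documents, and it would let any delay be compared across meals and genetic categories. All magnitudes rest on the assumed curve shape, lags and SDs, and larger differential delays would have larger effects.

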#### N/A

Describe how risks to subjects are minimized, for example, by using procedures which are consistent with sound research design and which do not unnecessarily expose subjects to risk or by using procedures already being performed on the subject for diagnostic or treatment purposes.

This study has been designed to reduce participant burden as much as possible while allowing for the robust data/specimen collection necessary to obtain predictive measures of dietary responses. All clinical procedures are routine and carry minimal risk, but are voluntary and participants can withdraw consent at any time.

The risks associated with collecting blood anthropometrics and questionnaires, present minimal risks. Total blood volume is 134ml at the point it reaches the lab, and a total of 170 ml taken from participant. As this is below 300ml over at least 6 hours, this does not result in added risk. Normal blood donation volume is 450-500ml. If nursing staff have any reason to be concerned with this volume of blood draw for any individual participant then they will discharge the participant. A total of 170 ml is calculated as 134ml for sampling, plus up to 36 mL discarded when removing flush from the cannula (4mls at each blood draw except at baseline to remove the flush so 4mlx9=36ml). Randomized study IDs will be assigned to participants to protect the patients' sensitive health information. Since these patients are healthy no adverse events are anticipated, however given that there is a dietary intervention involved participants will be monitored closely by study staff for possible adverse events during the visit day.

Describe explicitly the methods for ensuring the safety of subjects. Provide objective criteria for removing a subject from the study, for example, objective criteria for worsening disease/lack of improvement and/or unacceptable adverse events. The inclusion of objective drop criteria is especially important in studies designed with placebo control groups.

Participants can withdraw their consent at any time during the course of the study without giving any reason by contacting the study contact number. Similarly, the participant can withdraw their consent for the continued retention and use of their samples even after they have been collected, without giving a reason. Reason for discontinuation from the study will be asked about sensitively and recorded.

If a subject withdraws consent to the use of donated biological samples, any retained samples will be disposed of/destroyed. If these samples have already been used for data analysis (e.g. sequencing or metabolite measurement) it will not be possible to destroy this data and it will remain as a part of the study, but any data that is retained will be anonymized.

The Principal Investigator:

- Will ensure subjects' withdrawal of informed consent is recorded. Will ensure that biological samples from that subject, if stored at the study site, are immediately identified, disposed of/destroyed and the action documented.
- Will ensure that the laboratory(ies) holding the samples is/are informed about the withdrawn consent immediately and that samples are disposed of/destroyed and the action documented.

All participants must consume the baseline breakfast and provide baseline fasting bloods. Failure to meet these two requirements will result in termination of continued study participation as other endpoints will be unevaluable. If any other sample collections, dietary interventions, or blood timepoints are missed or unable to be completed, the subjects may continue with participation and these missing items will be logged by the study staff.

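### The reason given for ending participation after a missed fasting draw does not match the SAP: if breakfast is eaten, only meal 1 iAUC and change from fasting are lost

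*Protocol*

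**What the plan says.** In the protocol, the text on removing a subject (under Research Design and Methods) sets two requirements: "All participants must consume the baseline breakfast and provide baseline fasting bloods". It continues: "Failure to meet these two requirements will result in termination of continued study participation as other endpoints will be unevaluable". The reason given is about data; no safety ground is attached to it. The next sentence treats every other missed sample, dietary intervention or blood time point differently: "the subjects may continue with participation and these missing items will be logged by the study staff".

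The study procedures have participants "consume a set breakfast and an election lunch and provide blood samples at 9 time points", namely baseline, 30, 60, 120, 180 and 240 minutes, then lunch, then 270, 300 and 360 minutes. The clock is stated as "all minute intervals are relative to their first bite of the breakfast test meal".

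The SAP sets two separate windows: "The co-primary outcomes are response profiles of insulin and glucose after meal 1 (0-180 minutes) and meal 2 (240-360 minutes"). It adds: "Secondary outcomes will include incremental area under the curve of insulin and glucose after each meal, meal selection, and lipid levels at 240 minutes", counted from the first meal. Its mixed model adjusts for age, sex, BMI, three genetic principal components and time. The fasting value is not listed as a covariate. The SAP names no analysis set, gives no missing-data rule and does not mention terminated participants.

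**The concern.** A rule that ends participation because nothing else can be evaluated should agree with the list of endpoints. Here the SAP has a second co-primary window that starts four hours after breakfast with its own pre-meal sample, and several secondary outcomes that do not use the fasting value. If the reason is wrong for one of the two triggers, the study forgoes co-primary and secondary data it could have had, in a pilot of 30 people. The rule also sits oddly beside the sentence that follows it, which tolerates losses at least as large.

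**Working it through.** The plan states no figure to reproduce: the sample size of 30 comes without alpha, power, effect size or SD. The check therefore sets the endpoints against the schedule.

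**Step 1: count the samples.** The schedule is 0, 30, 60, 120, 180, 240, 270, 300, 360 minutes, which is 9 samples and agrees with the protocol. The meal 1 window (0-180) holds 5. The meal 2 window (240-360) holds 4, and the 240-minute draw precedes lunch.

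**Step 2: fasting draw missed, breakfast eaten.**

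| SAP outcome | What it uses | Status |
|---|---|---|
| Meal 1 profile (co-primary) | 0, 30, 60, 120, 180 min | 4 of 5 values remain and can enter the mixed model; change from fasting is lost |
| Meal 1 iAUC | 0 min as baseline | Not evaluable |
| Meal 2 profile (co-primary) | 240, 270, 300, 360 min | 4 of 4 values remain |
| Meal 2 iAUC | 240 min as baseline (assumed; the SAP does not define it) | Evaluable |
| Meal selection | Lunch choice | Observable |
| Lipids at 240 min | 240 min sample | Evaluable |

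Samples still obtainable: 9 - 1 = 8. The fasting sample is scheduled before breakfast, so if the rule is applied when the draw fails, all 8 go uncollected.

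**Step 3: breakfast not eaten.** All times run from the first bite, so there is no time origin. Meal 1 outcomes and lipids 240 minutes after the first meal do not exist. Lunch, and the choice of lunch, would follow a prolonged fast and would not be comparable with those of other participants. The protocol's reason largely holds here.

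**Step 4: compare with the rule for other missed items.** Missing the 240-minute draw loses the lipid outcome and the pre-lunch value for meal 2. Missing lunch loses the meal 2 response altogether. Both are only logged. Missing the fasting draw loses the meal 1 iAUC and one point of a five-point profile, yet ends participation.

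**Step 5: size.** Each termination removes 1/30 = 3.3% of participants from every later endpoint. To illustrate precision, assume a 15:15 split by genetic category, two-sided alpha 0.05 and 80% power (none of these is in the documents). The detectable difference in SD units is (1.960 + 0.842) × √(1/n1 + 1/n2):

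- none lost (15, 15): 2.802 × √0.1333 = 1.02
- 1 lost (15, 14): 2.802 × √0.1381 = 1.04
- 2 lost (15, 13): 2.802 × √0.1436 = 1.06
- 3 lost (15, 12): 2.802 × √0.1500 = 1.09

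One to three losses from one group therefore raise the detectable difference by about 0.02 to 0.06 SD.

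**The case against.** The best defence is that a valid fasting baseline and the standardized meal are the foundation of a postprandial study, and that requiring both is a common and reasonable choice. The co-primary meal 1 profile starts at 0 minutes, and the protocol's aims include metabolomic responses, where change from fasting may also matter. A failure to provide fasting blood may not be a skipped tube. The participant may have arrived unfasted, which would compromise the 30-180 minute values, or venous access may have failed, which would threaten later draws. The figure of 8 of 9 samples is thus an upper bound. These points stand. They limit the finding to a technically missed sample in a fasted participant who eats the breakfast. They do not rescue the statement that the other endpoints cannot be evaluated, because meal 2 has its own baseline.

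A reader might infer three stronger things, none of which the documents support:

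- **That the same criticism applies when breakfast is not eaten.** It does not, for the reasons in step 3.
- **That the rule biases the comparison by genotype**, because participants are recalled for genotypes that influence intake and might leave the breakfast for that reason. No rate or direction is given. The eligibility criteria already exclude vegans, people with an eating disorder and people unwilling to eat the study foods. That route also concerns an uneaten breakfast, not a missed draw.
- **That collected data are discarded.** The rule stops further participation; it does not say that data already obtained are removed.

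**Conclusion.** The point holds for one trigger only. When the fasting draw alone is missed and breakfast is eaten, the protocol's stated reason contradicts its own schedule and the SAP's endpoints, and the rule is out of line with the tolerance shown to other missed items. The result is that evaluable co-primary and secondary data are not collected.

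The size is unknown and probably small: the documents give no expected number of missed fasting draws, and people who cannot fast are excluded at screening. The conclusion assumes that the 240-minute sample is the baseline for meal 2 iAUC, that later draws are obtainable, and that the missed draw is unrelated to the value it would have shown. It is worth correcting because each participant is 3.3% of the pilot and the correction is to the text.

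**What to change.** Reconcile the protocol's text on removing a subject with the SAP by replacing the blanket statement with evaluability by endpoint:

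- **Fasting sample technically missed, breakfast eaten:** meal 1 iAUC and change from fasting are not evaluable. Any 30-180 minute values, meal 2 profile, meal 2 iAUC, 240-minute lipids and meal selection that are obtained belong in the analysis set.
- **Participant not fasted:** state separately which meal 1 values count as evaluable.
- **Breakfast not eaten:** no change is asked for.

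In the SAP, define the analysis set for each meal, name the baseline used for each iAUC, and report terminations and their reasons by genetic category.

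Whether a participant goes on with the visit, for safety, burden or failed venous access, is for the investigators, and no rule is proposed here. If termination is kept on such grounds, the protocol should state those grounds in place of unevaluability.

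The cost is a reworded protocol paragraph and a few lines in the SAP. The downside is that denominators will differ by endpoint and must be shown in each table.
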